## 6.2. Selection of Study Population

Children falling within the following profile will be entered into the study: females age 2 to 8 years (inclusive) or males age 2 to 9 years (inclusive); confirmed diagnosis of CPP within 12 months of Baseline Visit (Day 0) but have not received prior GnRH agonist treatment for CPP; pubertal-type LH response following an Abbreviated GnRHa Stimulation Test before treatment initiation  $> 5$  mIU/mL; clinical evidence of puberty, defined as Tanner stage  $\geq 2$  for breast development in females or testicular volume  $\geq 4$  mL in males; and difference between bone age (Greulich and Pyle method) and chronological age  $\geq 1$  year.

## 6.3. Treatment and Random Assignment

This single arm study does not require the use of randomization. All subjects will be treated identically with respect to procedures carried out in either Part A or Part B of this study.

## 6.4. Treatment Masking (Blinding)

This is an open label study. Neither subjects, the sponsor or study staff are blind to the treatment.

## 6.5. Analyses and Reporting

In this study both *a) the need for an adaptive change in study design* and *b) treatment efficacy* will be based on an absolute descriptive finding rather than an inferential significance level.

## 6.6. Criterion for Treatment Efficacy

If suppression in  $\geq 85\%$  of the first 16 subjects to be evaluated at Month 6 is found, the study will terminate under Part A without the invocation of Part B as a follow-on adaptive dosing schedule. If study termination under Part A occurs, the criterion variable for adaptive change applied to the first 16 children at six months, namely, percent of children with  $< 4$  mIU/mL suppression, will *also* function as the primary outcome variable when applied to all children in the study. As was the case for evaluating the requirement for an adaptive change in design, an absolute descriptive rather than inferential statistical outcome will be used to assess efficacy for the primary outcome variable. Using the same variable as that used to omit or invoke Part B, efficacy will be claimed if  $\geq 80\%$  of the children exhibit  $< 4$  mIU/mL suppression.

If suppression in approximately  $< 85\%$  of the first 16 subjects ( $N \geq 3$ ) to be evaluated at Month 6 is found, the study will be adapted and Part B will be invoked. As would be the case if the study were to terminate with Part A, the percent of subjects with  $< 4$  mIU/mL suppression will serve as the primary outcome variable under Part B. If  $< 4$  mIU/mL suppression in  $\geq 80\%$  of the children in the study at Visit 11 (Month 21) is found, efficacy will be claimed. The primary variable if only Part A of the study were carried out will then become a secondary outcome variable.

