8. INVESTIGATIONAL PLAN

8.1 Overall Study Design and Plan

This will be an adaptive design study conducted in two parts as illustrated in [Figure 1](#).

Figure 1 Study Design

Subjects will only receive Injections #3 and #4 if Part B is conducted, based on Part A interim data.

Part A:

This will be a multi-center, open-label, single-arm 12-month study. Pediatric subjects with CPP will receive their first SC injection of the study drug (leuprolide acetate 45 mg for injectable suspension) at the start of the study and the second injection at the Month 6 visit. Subjects will return to the clinic periodically for 12 months from the start of dosing for assessment of efficacy, safety and pharmacokinetics (PK).

An independent DSMB will review the safety of the drug throughout the study.

An interim analysis of LH suppression from the GnRHa stimulation test results will be conducted after approximately 40% of the 40 subjects anticipated to complete 6 months of assessments have data through the Month 6 visit (N = approximately 16). Based on this analysis, if LH concentrations after the GnRHa stimulation test are suppressed to < 4 mIU/mL in < 85% of these subjects, then Part B of the study will be invoked. All subjects still undergoing therapy in the Part A of the study and those yet to enroll in the study, if eligible, will be asked to participate in the Part B extension study for additional dosing at shorter intervals. The progression to Part B extension will be based on evaluations by the DSMB and Sponsor.

Part B Extension:

This part of the study will be conducted based on analysis of interim data from Part A.

NOTE: Because the interim analysis will only provide data from a very small sample size informing the decision to conduct Part B of the study with a 5-month dosing interval, **ALL** new subjects being enrolled into the study will begin with Part A of the study with the first 6-month dosing interval before proceeding to Part B. In this manner, there will be adequate data for comparison of dosing intervals for assessment of optimal efficacy.

If invoked, this will be a multi-center, open-label, single-arm extension following Part A. Only subjects who have received the second injection of the study drug in Part A will be permitted to

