9.2 Statistical Methods

The purpose of this study is to demonstrate suppression of LH at a level of < 4 mIU/mL at 30 minutes after GnRHa stimulation in a majority of subjects ($\geq 80\%$) who are treated with leuprolide acetate 45 mg in an injectable suspension. Descriptive outcomes for the primary and secondary efficacy variables will be used to evaluate the efficacy of this treatment.

If suppression in $\geq 85\%$ of the first 16 subjects to be evaluated at Month 6 is found, the study will terminate under Part A without the invocation of Part B as a follow-on adaptive dosing schedule. If study termination under Part A occurs, the criterion variable for adaptive change applied to the first 16 patients at six months, namely, percent of patients with < 4 mIU/mL suppression, will *also* function as the primary outcome variable when applied to all patients in the study. As was the case for evaluating adaptive change in design, an absolute descriptive rather than inferential statistical outcome will be used to assess efficacy for the primary outcome variable. Efficacy will be claimed if $\geq 80\%$ of the subjects exhibit < 4 mIU/mL suppression.

If suppression in $< 85\%$ of the first 16 subjects to be evaluated at Month 6 is found, the study will be adapted and Part B will be invoked. As would be the case if the study were to terminate with Part A, the percent of subjects with < 4 mIU/mL suppression will serve as the primary outcome variable under Part B. If < 4 mIU/mL suppression in $\geq 80\%$ of the patients in the study at Visit 11 (Month 21) is found, efficacy will be claimed.

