9.2.4 Interim Analysis

An interim analysis of LH suppression from the GnRHa stimulation test results will be conducted after approximately 40% of the 40 subjects anticipated to complete 6 months of assessments have data through the Month 6 visit (N = approximately 16). Based on these data, if LH concentrations after the GnRHa stimulation test are suppressed to < 4 mIU/mL in < 85% of these subjects, then Part B of the study will be invoked. All subjects still undergoing therapy in the Part A of the study and those yet to enroll in the study, if eligible, will be asked to participate in the Part B extension study for additional dosing at shorter intervals. The progression to Part B extension will be based on evaluations by the DSMB and Sponsor. Subjects that progress to Part B of the study will be provided information about Part B in an ICF and Assent Form (if required), which will be signed by appropriate parent/guardian(s) and the subject.

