## 6.7. Sample Size Determination

The expected final sample size is between 25 and 50 subjects, depending on dropout rate and whether the study is prolonged by the inclusion of Part B. If for the final sample size  $\geq 80\%$  of

subjects exhibit < 4 mIU/mL suppression, efficacy will be claimed. It is actually expected that 85% to 90% response is likely. The table immediately below shows the lower one-sided 95% confidence limits for final sample sizes varying from 25 to 50 in increments of five subjects under the expectations of 85% suppression and 90% suppression.

Table 4 Numeric Results for One-Sided Lower-Limit Confidence Intervals for One Proportion Confidence Interval Formula: Simple Asymptotic with Continuity Correction

Confidence Level	Sample Size (N)	Actual	Proportion (P)	Lower Limit	Upper Limit
		Distance from P to Lower Limit			
0.950	25	0.137	0.850	0.713	1
0.950	25	0.119	0.900	0.781	1
0.950	30	0.124	0.850	0.726	1
0.950	30	0.107	0.900	0.793	1
0.950	35	0.114	0.850	0.736	1
0.950	35	0.098	0.900	0.802	1
0.950	40	0.105	0.850	0.745	1
0.950	40	0.091	0.900	0.809	1
0.950	45	0.099	0.850	0.751	1
0.950	45	0.085	0.900	0.815	1
0.950	50	0.093	0.850	0.757	1
0.950	50	0.080	0.900	0.820	1

In Table 4 the lower one sided confidence limit never falls below 70%. Suppression to < 4 mIU/mL in 70% of the subjects is considered to be clinically important by TOLMAR. Thus the sample size is thought to be adequate.

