**19.4. Appendix 4: SAP Modifications (TBD)**

Change Log			
Version No.	SAP Date	Change / Revision	Author(s)
1.1	06 Jan 2017	Administrative Changes: 
 
• Section 6.1.1: Revised language to clarify criteria for adaptive change in design.
 
• Section 6.6: Added “approximately” and “(N ≥ 3)” to clarify actual value equating to 85% of 16 subjects.
 
• Section 7: Added “are the four forms”
 
• Signature Page: Added “[name], Clinical Trials Manager” to replace “[name], Statistician II”
 
	[REDACTED] (Tolmar), [REDACTED] (Tolmar)
1.2	02 February 2017	Administrative Changes: 
 
• Table 4: removed final column “Distance from P to Limit if P = 0.5”
 
• Section 7: Removed “are the four forms” addition made in version 1.1 for clarity and accuracy. Added “s” to “instance”
 
• Table 5: Moved “X” for Baseline Safety and Safety row under “Categorical Descriptive Analysis” column from “Continuous Descriptive Analysis” column
 
	[REDACTED] (Tolmar), [REDACTED] [REDACTED] (EMB)
1.3	06 June 2018	Administrative Changes: 
 
• Section 8.3.2 – Bullet #4: Removed “/PD” since the analyte is leuprolide.
 
• Section 10.2: Removed “PK/” typo to align definition of ITT to the Protocol.
 
• Footer pages 14-43: Revised page stamp be consistent with pages 1-13 and throughout document.
 
• Signature Page: Added [name]
 
	[REDACTED] (Tolmar), [REDACTED] [REDACTED] (Tolmar)

1.4	04 Sep 2018	Administrative Changes: 

• Section 5.2 – Bullet #5 was Added: “Assess growth velocity of height in cm/year after the first treatment administration.”

• Section 8.2.2 – Bullet #3 was Added; “The growth velocity of height in cm/year at each available post-baseline measurement. Growth velocity is defined for each visit as (change from Baseline)/[(number of weeks since Baseline)/52]

	██████████ (EMB)
-----	-------------	--	------------------

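### The Month 6 percentage includes the interim children whose result decides whether Part B runs, so within each branch it is shifted; the 5- versus 6-month comparison is the main casualty

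*SAP*

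**What the plan says.** An interim look is taken when about 16 children, 40% of the 40 expected to complete six months, have Month 6 data (Protocol 9.2.4). If LH is "suppressed to < 4 mIU/mL in < 85% of these subjects, then Part B of the study will be invoked". The SAP gives the trigger as a count, three or more children not suppressed, and its change log says this was done "to clarify actual value equating to 85% of 16 subjects". So 14/16 (87.5%) keeps the trial in Part A and 13/16 (81.25%) leads to Part B.

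If Part A stands alone, the interim variable will also "function as the primary outcome variable when applied to all children in the study" (SAP 6.6; Protocol 9.2 has the same sentence for patients). Efficacy is claimed at 80% or more. If Part B runs, the primary endpoint moves to Month 21, and for Month 6: "The primary variable if only Part A of the study were carried out will then become a secondary outcome variable" (SAP 6.6).

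Efficacy rests on the ITT population (SAP 10.3) with available data (SAP 12). Nothing separates the interim children or allows for the selection. For precision, SAP 6.7 states: "The table immediately below shows the lower one-sided 95% confidence limits for final sample sizes varying from 25 to 50". On the interval question, Protocol 8.1 has all new subjects begin with a 6-month interval and adds: "In this manner, there will be adequate data for comparison of dosing intervals for assessment of optimal efficacy".

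**The concern.** The first 16 results have two uses. They decide which role Month 6 takes, and they then count in the Month 6 figure reported in that role. If Part A stands alone, those 16 are known to be at least 87.5% suppressed. If Part B runs, they are known to be at most 81.25% suppressed. The other children carry no such selection, but they are only 60% of a sample of 40.

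Two readings are affected. One is the Part A percentage set against the 80% bar. The other is the comparison of 5- and 6-month dosing, a secondary objective (Protocol 7.2, SAP 5.2) that can be addressed only if Part B runs, which is when Month 6 has been selected low. In that branch Part A Visits 7 and 8 are not done (footnote to the Part A schedule), and the Month 9 and Month 11 tests fall three and five months after Injection #2. For a child entering Part B, Month 6 is the only stimulation test six months after an injection. A regression-to-the-mean gap between Month 6 and Month 21 could then be read as an advantage of the shorter interval.

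**Working it through.** **The plan's own figures.** SAP Table 4 uses lower limit = p − [1.645·√(p(1−p)/n) + 1/(2n)]. For n = 40, p = 0.85: 0.85 − (1.645 × 0.0565 + 0.0125) = 0.745, as printed. All 12 limits reproduce. The formula assumes one sample of fixed size with no interim selection. Also 0.40 × 40 = 16 and 0.85 × 16 = 13.6, so at least 14 of 16 must be suppressed to stay in Part A.

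**Inputs.** Interim n = 16 (Protocol 9.2.4); Part A N = 40 (Protocol 9.1), with final N from 25 to 50 (SAP 6.7); expected rate 85% to 90% (SAP 6.7); claim at ≥ 80%, i.e. ≥ 32/40.

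**Assumptions.** Independent children, the same true rate p in all, rule applied as written.

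**Shift within a branch.** Let X ~ Bin(16, p). Part A stands alone if X ≥ 14. Then

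E[Month 6 % | branch] = (E[X | branch] + (N − 16)p) / N.

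At p = 0.85:
- P(X ≥ 14) = 0.277 + 0.210 + 0.074 = 0.561.
- E[X | X ≥ 14] = 14.64, so the Month 6 figure is (14.64 + 24 × 0.85)/40 = 87.6%, or +2.6 points.
- E[X | X ≤ 13] = 12.27, so it is (12.27 + 20.4)/40 = 81.7%, or −3.3 points.
- Average over branches: 0.561 × 87.6 + 0.439 × 81.7 = 85.0. Overall there is no bias.

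| True rate (N = 40) | P(Part A alone) | Month 6 expected, Part A alone | Month 6 expected, Part B runs |
|---|---|---|---|
| 75% | 0.197 | 80.9% (+5.9) | 73.5% (−1.5) |
| 80% | 0.352 | 84.2% (+4.2) | 77.7% (−2.3) |
| 85% | 0.561 | 87.6% (+2.6) | 81.7% (−3.3) |
| 90% | 0.789 | 91.2% (+1.2) | 85.4% (−4.6) |

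Over N = 25 to 50 at a true 85%, the shift runs from +4.2 to +2.1 points (Part A alone) and from −5.3 to −2.7 (Part B runs).

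**Chance of a Month 6 claim.** With Y ~ Bin(24, p), the joint probability is P(X ≥ 14 and X + Y ≥ 32). The conditional one divides it by P(X ≥ 14).

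| True rate | Single look, P(≥ 32/40) | Given Part A alone | Joint: gate passed and claim |
|---|---|---|---|
| 70% | 11.1% | 44.0% | 4.4% |
| 75% | 30.0% | 66.4% | 13.1% |
| 80% | 59.3% | 85.5% | 30.1% |
| 85% | 86.5% | 96.4% | 54.1% |

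**Interval comparison.** If both intervals truly suppress 85%, the all-subject Month 6 figure is still expected at 81.7% when Part B runs, 3.3 points in favour of 5 months with no real difference. At 90% the gap is 4.6 points.

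**Without the interim children.** The remaining 24 have expectation p in either branch. The standard error at 85% is √(0.85 × 0.15/24) = 7.3 points, against √(0.85 × 0.15/40) = 5.6.

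**The case against.** The strongest reply is that the plan is descriptive: the Part A decision is an observed percentage, no inferential testing is planned (SAP 11.1), and Table 4 is a planning table rather than a results interval. The last point stands, so nothing here rests on the coverage of an interval that the SAP does not commit to. But the description is turned into a decision at 80%, and a descriptive percentage is shifted by selection as much as any other.

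A reader might infer that a regimen truly below 80% is likely to be declared effective. The plan's figures do not support that. At a true 75% the conditional chance is 66.4%, but Part A stands alone in only 19.7% of such trials, so the joint chance is 13.1% against 30.0% for a single look. At 70% even the conditional chance is below one half. The gate makes a false Month 6 claim rarer. A reader might also infer a higher overall rate of false claims. Any such rise comes from the second opportunity at Month 21, which is a separate matter that this fix does not touch.

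Three further points stand. At the expected 85% to 90%, the Part A shift is small beside a standard error of 5.6 points (at 85%), and the −4.6 points at 90% arise in a branch with probability 0.21. The rule is not strictly binding, because progression rests on DSMB and sponsor evaluation (Protocol 9.2.4) and the SAP writes approximately. Finally, the tilt in the interval comparison depends on which children are compared. The SAP's only example (SAP 7) sets visits after injection 2 against visits after injection 4. SAP 6.1.1 admits to Part B those enrolled children who have not had a second injection, whereas interim children receive it at the Month 6 visit. On that text a within-child comparison in Part B would avoid the selection. Protocol 8.1.1 and 9.2.4 are broader and would let interim children in up to Month 11.

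**Conclusion.** The point holds as a moderate bias conditional on the branch. A trial is reported from the branch it took, so the zero average over branches does not help the reader of the result. At N = 40 and the plan's expected 85% to 90%, the shift is +2.6 to +1.2 points if Part A stands alone and −3.3 to −4.6 if Part B runs. It is larger with a smaller final N and, for Part A alone, when the true rate is near or below 80%.

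The consequence that matters most is for the 5- versus 6-month objective, where an all-subject Month 6 figure favours 5 months without any true difference. The 80% rule for Part A needs a caveat and a sensitivity estimate, not a new criterion. When Part B runs, the efficacy claim rests on Month 21 and this shift does not touch it. All sizes assume independent children with a common true rate and the 14/16 rule applied as written.

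**What to change.** - **SAP 6.6 and 8.2.1:** state that the Month 6 percentage will also be presented for ITT subjects not in the interim analysis (about 24), as a sensitivity estimate beside the unchanged all-subject primary.
- **SAP 7:** state that, if Part B is invoked, the 5- versus 6-month comparison will use Month 6 results of non-interim subjects, paired within child with Month 21 where both exist.
- **SAP Table 4:** add a note that its limits assume a fixed sample with no interim selection.
- **SAP 6.1.1 against Protocol 8.1.1 and 9.2.4:** reconcile which Part A subjects may enter Part B, since this decides whether interim children appear in the Month 21 data.

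The cost is one table row and a few sentences; no visit or criterion changes. The added estimate is less precise: the standard error is 7.3 instead of 5.6 points at 85%, and a limit of the Table 4 type at 85% is about 0.709 with 24 children, against 0.745 with 40. It may also look less favourable. At a true 85%, 24 children reach 80% (20/24 or more) with probability 0.713, so a figure below 80% in this row alone should not be read as failure.

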8.1.1 Duration of Study

In Part A, after a 28-day screening period, each subject will participate in the study for 48 weeks. Six months after Injection #1 in Part A, subjects will receive Injection #2 of the study drug. There will be a total of 7 study visits during Part A for a total duration of approximately 12 months.

Part A of the study is expected to take up to 24 months from first subject first visit (FSFV) to last subject last visit (LSLV), if Part B is not conducted.

After the interim analysis, if the DSMB and the Sponsor make the decision to conduct Part B of the study then all currently enrolled eligible subjects and all newly enrolled subjects will receive a total of 4 injections of the study drug. Subjects who have gone beyond the Month 11 visit will not be considered eligible to participate in Part B extension as they would be considered to be out-of-window for Injection #3.

If Part B of the study is invoked, the study length (for both Parts A and B) will be expected to be extended for approximately 10 more months for a total of approximately 34 months from FSFV (Injection #1) to LSLV. With the addition of Part B, commitment of each subject in the study will increase from 12 months to 21 months.

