8.6.17 Part B, Visit 10 (~Month 20/Week 76 ± 7 days)

1. Query subject or parent “How have you felt in the last two weeks?” or “How has your child felt in the last two weeks?” Complete [Table 4](#)
2. Vital signs - measured prior to any blood draws

3. AE and concomitant medications assessments
4. Physical Examination—directed
5. Tanner stage
6. Height and weight
7. Blood samples for basal LH, FSH, testosterone/estradiol concentrations
8. Blood sample for basal serum leuprolide concentrations
9. Schedule/confirm next visit

8.6.18 Part B, Visit 11 (~Month 21/Week 80 ± 7 days)—End of Treatment or Early Discontinuation

1. Query subject or parent “How have you felt in the last two weeks?” or “How has your child felt in the last two weeks?” Complete [Table 4](#)
2. Vital signs - measured prior to any blood draws
3. AE and concomitant medications assessments
4. Physical Examination—complete
5. Tanner stage
6. Height and weight
7. X-ray of non-dominant hand and wrist
8. Urine pregnancy test, females only
9. Clinical laboratory assessments (hematology, chemistry) as per [Appendix 13.1](#)
10. Urine for urinalysis, performed using dipstick supplied by Sponsor
11. Blood samples for basal LH, FSH, testosterone/estradiol concentrations PRIOR to the GnRHa stimulation
12. Blood sample for basal serum leuprolide concentrations PRIOR to the GnRHa stimulation
13. GnRHa stimulation: aqueous leuprolide acetate 20 µg/kg body weight administered SC
14. Blood samples for LH, FSH, testosterone/estradiol concentrations 30 ± 5 minutes AFTER the GnRHa stimulation test

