9.1 Sample Size Determination

To determine the percentage of subjects with suppression of serum LH to < 4 mIU/mL following treatment with leuprolide acetate 45 mg, it is estimated that approximately 40 subjects would be sufficient for assessment of Part A and approximately 27 subjects for Part B, if invoked. Approximately 60 subjects may be enrolled in the study in order to get an appropriate number of assessable subjects.

The sample size was pragmatically determined based on the clinical trial size and response rate of other GnRH antagonists studies in CPP subjects.

The descriptive finding that will conclude efficacy is that ≥ 80% of subjects will exhibit < 4 mIU/mL LH suppression. This is conservative, since the dropout rate is unknown, and it is anticipated that the percent of subjects suppressed is likely to be at least 85%. Thus, 85% suppression or 90% suppression might be reasonably expected. However, the drop out in this

study could be slightly more than 50%, if Part B is invoked, thus depending on whether only Part A is carried out or Part B is invoked, the final available sample size after drop out could vary between 25 and 50 subjects given the planned recruitment of 60 subjects. Suppression to < 4 mIU/mL in approximately 70% of the subjects is considered to be clinically important if the full expectations of all drop-out are completed. Thus, the study is thought to have a sufficient number of subjects. If 85% of subjects enrolled are found to be suppressed we would expect a lower 95% one sided confidence interval under a fully realized drop out scenario (ie, 25 final subjects) of slightly more than 70%.

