### 10.2. ITT population

The intent to treat (ITT) population will consist of subjects providing consent/assent who received at least one dose, fulfilled the protocol eligibility criteria, and provided at least one PD laboratory assessment post dosing.

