### 10.3. PP population

The per protocol population (PP) will consist of subjects who have received at least one dose of the study medication and have fulfilled the protocol in terms of eligibility, interventions and outcome assessments for at least 6 months.

The table below cross-classifies the various endpoints with the analysis populations.

Table 6 Cross-classification of Various Endpoints with the Analysis Populations

Type of Endpoint	Study Population		
	Safety	Intent to Treat	Per Protocol
Baseline Endpoints		X	X
Primary Efficacy Endpoint		X	X
Secondary Efficacy Endpoint		X	X
Exploratory Efficacy Endpoints		X	X

Safety Endpoints	x		
PK Endpoints		x	

Efficacy will be based on findings using the ITT population. It is noted that for some variables the ITT and PP populations may be identical.

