## 12. IMPUTATION AND MISSING DATA

Unless otherwise indicated, imputation of missing data will not be performed for baseline, efficacy and safety variable values. Each table containing an analysis that reflects an outcome at a given time point in the study will contain only subjects in the analysis population under examination who have data available at that time point.

If a missing concentration datum is surrounded by non-missing values, interpolation will be used in the calculation of AUC, Cmax and Tmax. Otherwise, the nearest non-missing point in time will be used.

If missing date and time values are evident in data not used to develop PK parameters, the following missing date and time algorithm may be applied.

For partial start date/time:

- If the year is unknown, then the date will not be imputed and will be assigned a missing value.
- If the month is unknown, then:
  - If the year matches the year of the dose of study drug date, then the month and day of the dose of study drug date will be imputed.
  - Otherwise, 'January' (01) will be assigned.
- If the day is unknown, then:
  - If the month and year match the month and year of the dose of study drug date, then the day of the dose of study drug date will be imputed.
  - Otherwise, '01' will be assigned.
- If the day is unknown, then:
  - If the month and year match the month and year of the dose of study drug date, then the day of the dose of study drug date will be imputed.
  - Otherwise, '01' will be assigned.
- If the time is unknown, then:
  - If the date (day, month, and year) matches the date of the dose of study drug date, then the time of the dose of study drug time will be imputed.
  - Otherwise, '00' will be assigned.
- For partial stop date/time:
  - If the year is unknown, then the date will not be imputed and will be assigned a missing value.
  - If the month is unknown, then 'December' (12) will be assigned.
  - If the day is unknown, then the last day of the month will be assigned.
  - If the time is unknown, then the last time of the day will be assigned.

If time to an event were needed when only the hour, and not the minutes, are reported for the time of the event, then the minutes will be set to zero.

Any deviations from the implementation of the missing date and time algorithms will be documented in the dataset documentation and final report.

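### If Part B is invoked, the Month 21 efficacy claim carries an ITT label but counts only children with a Month 21 test, so children who leave after Injection #3 drop out of the 80% rule

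*SAP*

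**What the plan says.** Efficacy is decided on a point estimate. SAP 6.5 bases it on an "absolute descriptive finding rather than an inferential significance level". For Part B, SAP 6.6 adds that if suppression (stimulated LH below 4 mIU/mL) in at least 80% "of the children in the study at Visit 11 (Month 21) is found, efficacy will be claimed".

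On who is counted, the SAP says two things:
- SAP 10.3, below Table 6: "Efficacy will be based on findings using the ITT population". SAP 10.2 defines ITT as consenting children who "received at least one dose, fulfilled the protocol eligibility criteria, and provided at least one PD laboratory assessment post dosing". The first such sample is due one hour after Injection #1 (Protocol Table 2), so nearly every eligible dosed child qualifies.
- SAP 12: each table for a time point "will contain only subjects in the analysis population under examination who have data available at that time point". Protocol 9.2.5 and SAP 12 rule out imputation of efficacy data.

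On attrition, Protocol 9.1 concedes that dropout in this "study could be slightly more than 50%, if Part B is invoked". The Synopsis expects about 40 evaluable children at Month 6 and about 27 participating in Part B. Protocol 8.1.2 expects about 27 to complete Month 21.

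On entry, Protocol 8.1.1 states: "Subjects who have gone beyond the Month 11 visit will not be considered eligible to participate in Part B extension". SAP 6.1.1 instead names current subjects who have not yet had a second injection, plus future subjects.

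On early exit, Part B Visit 11 (Protocol 8.6.18) is titled "End of Treatment or Early Discontinuation" and includes a stimulation test. SAP 12.3 assigns early-termination data to a visit for safety variables only.

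**The concern.** The ITT label tells the reader that every eligible, dosed child bears on the result. The computation uses only children tested at Month 21. Some of the gap is administrative: a child who was past Month 11 when Part B was invoked could never contribute, and that exclusion says nothing about response. A child who entered Part B and then left is different. The study is open-label. The Month 3 discontinuation rule presupposes that sites see stimulated LH. Further stimulation tests follow at Months 11 and 16, and discontinuation at the investigator's discretion is allowed (Protocol 8.2.3). Leaving can therefore depend on poor suppression, and such a child is removed from the rate instead of lowering it.

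With about 27 children and a bare 80% threshold, a few such removals can decide whether efficacy is claimed. The per-protocol set is no safeguard: it requires outcome assessments for at least 6 months only, and the same available-data rule applies to it.

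**Working it through.** **1. The plan's own figure.** SAP Table 4 gives a one-sided 95% lower limit of 0.713 for 85% suppression with 25 final subjects. Formula: p − 1.645·√(p(1−p)/n) − 1/(2n) = 0.85 − 1.645·√(0.85·0.15/25) − 0.02 = 0.7125. All twelve rows agree within 0.001. The sample-size argument thus already treats children remaining at the end as the denominator.

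**2. Expected attrition.** From about 60 to 40 at Month 6 to 27 at Month 21: 20 are lost before completing Month 6 and 13 afterwards (13/40 = 32.5%). Overall 33/60 = 55.0%, in line with Protocol 9.1. The 13 mix children who never enter Part B with children who enter and leave, and the documents do not split them. The Synopsis uses 27 for participants and Protocol 8.1.2 uses 27 for completers, so no allowance for loss after entry is stated.

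**3. Minimum pass.** 0.80 × 27 = 21.6, so 22 are needed: 22/27 = 81.5% passes and 21/27 = 77.8% fails.

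**4. Effect of leavers.** Hold 27 children with a Month 21 test, of whom x are suppressed, and add k children who received Injection #3, have no Month 21 test and count as not suppressed. Rate = x/(27 + k). Assumption: k from 1 to 4.

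| Suppressed, of 27 tested | k = 0 | k = 1 | k = 2 | k = 3 | k = 4 |
|---|---|---|---|---|---|
| 22 | 81.5% | **78.6%** | 75.9% | 73.3% | 71.0% |
| 23 | 85.2% | 82.1% | **79.3%** | 76.7% | 74.2% |
| 24 | 88.9% | 85.7% | 82.8% | 80.0% | **77.4%** |

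Bold marks the first failing value in each row.

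**5. How likely a thin margin is.** Binomial, n = 27. Exactly 22 suppressed has probability 19.1%, 17.2% and 8.0% at true rates of 80%, 85% and 90%. For 22 or 23 it is 17.2% + 21.1% = 38.3% at 85% (overall chance of passing 79.0%) and 8.0% + 15.6% = 23.5% at 90% (passing 95.3%), before rounding of the terms.

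**6. How likely Part B is.** It is invoked when at most 13 of 16 are suppressed (13/16 = 81.3%; 14/16 = 87.5%). The probability is 44% at a true rate of 85% and 21% at 90%, the range the SAP expects.

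**7. Why the full ITT set cannot be the denominator.** If ITT were 60 and all untested children counted as failures, even 27/27 would become 27/60 = 45.0%. With ITT of 50 or 40 the ceiling is 54.0% or 67.5%. The 80% rule could not be met, largely for administrative reasons.

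**The case against.** The available-data rule is stated openly, and other provisions give partial transparency. SAP 16 compares children without Month 21 data with the rest at baseline. SAP 14.3 tabulates terminations by reason. The Month 6 rate stays as a secondary endpoint, suppression is reported at the other tests, and SAP 7 requires numerator and denominator to be shown. The only LH-based discontinuation criterion is at Month 3; Part B has none. Counting missing tests as failures is itself a convention, and it understates the rate when children leave for unrelated reasons. All of this stands, but none of these provisions changes the percentage compared with 80%.

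Four stronger readings are tempting, and the documents do not support them:
- **More than half of the ITT children can never have a Month 21 test.** The 60 may include children who were only screened (Synopsis), and enrolment is counted from consent and subject number (Protocol 8.6). With 27 tested, the untested share is 55% if ITT is 60, 46% if 50 and 32.5% if 40. Expected dropout is also not a bar, and about 20 of the 33 are lost before Month 6 completion.
- **One child decides the result.** With 27 tested children, that is true only at 22/27.
- **The bias consists exactly of children in whom the shorter interval failed.** LH-driven withdrawal is possible, but it is not shown.
- **An early-exit test can freely pass as Month 21.** SAP 8.2.1 sets the test five months after the fourth injection and SAP 12.3 moves only safety data, so the text already leans against this. What is missing is an explicit sentence.

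**Conclusion.** The point holds for the Part B claim only. The Month 21 result is an available-case result under an ITT label, and children who receive Injection #3 and then leave are excluded from the 80% decision. The likely direction is upward if leaving is related to suppression. The size depends on the margin: one leaver reverses 22/27, two reverse 23/27 and four reverse 24/27. This rests on 27 tested children, on 1 to 4 leavers after Injection #3 (an assumption, since the plan gives no figure), and on counting them as not suppressed. It does not rest on the overall 55%, most of which arises before Month 6 or may come from children who never enter Part B. The remedy is cheap and makes the decision rule less open to selective loss, so it should be adopted.

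**What to change.** In SAP 6.6, 8.2.1 and 12:
- Define the Part B primary denominator as all ITT children who received Injection #3, and name it as that set, not as the full ITT population.
- Count a child in that set without a stimulated LH in the Month 21 window as not suppressed.
- State that an early-discontinuation test is not used as the Month 21 result.
- Report the observed-case percentage as a sensitivity analysis.
- Tabulate ITT children who did not enter Part B by reason (past Month 11, declined, withdrawn) with their Month 6 result.

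Reconcile Protocol 8.1.1 with SAP 6.1.1 on who may enter Part B, because the new denominator depends on it. Fix the Month 21 window at the same time: Table 3 places Injection #4 at Week 64 and Visit 11 at Week 80, which is 16 weeks, while the text says five months and the other five-month intervals (Weeks 24 to 44 and 44 to 64) span 20 weeks. These passages must be reconciled as well.

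Cost: SAP wording and one extra table, with no added visits, samples or treatment changes. The downside is a slightly less favourable percentage when children leave Part B for unrelated reasons; the observed-case figure beside it shows by how much.
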